13.0 TAS102 DRUG INFORMATION

Storage and Handling

- Store at 20°C to 25°C (68°F to 77°F); excursions are permitted from 15°C to 30°C (59°F to 86°F) [See USP Controlled Room Temperature].
- TAS102 LONSURF is a cytotoxic drug. Follow applicable special handling and disposal procedures. "OSHA Hazardous Drugs". OSHA. (http://www.osha.gov/SLTC/hazardousdrugs/index.html)
- If stored outside of original bottle, discard after 30 days.

14.0 STATISTICAL CONSIDERATIONS AND METHODOLOGY

14.1 Statistical justification

The primary endpoint will be the Neoadjuvant Response (NAR) Score. This is an established efficacy endpoint for phase II/III rectal cancer trial, offering an early indicator of treatment effectiveness (17). In table I, inclusion criteria, pre-operative therapy and the corresponding pCR rate of published phase II and phase III trials of total neoadjuvant chemotherapy are summarized. The wide range of reported pCR rates is a reflection of treatment efficacy and the pre-treatment tumor stage of eligible patients.

Table 11. Evidence for neoadjuvant chemotherapy in stage 11/111 rectai cancer.				
Study	Inclusion	Preoperative Therapy	Ν	pCR (95% CI)
Polish II (4)	High Risk	$5x5 \text{ RT} \rightarrow \text{FOLFOX4} \times 3$	261	16%
	T3/T4			
RAPIDO (2)	High Risk	CRT	460	Pending
		$5x5 \text{ RT} \rightarrow \text{CAPOX x } 6$	460	(19% full
				cohort)
Garcia-	Stage II/III	CRT	60	18% (10-30)
Aguilar(23)		CRT \rightarrow FOLFOX x2	67	25% (16-37)
		CRT \rightarrow FOLFOX x4	67	30% (19-42)
		CRT \rightarrow FOLFOX x6	65	38% (27-51)

Table 11. Evidence for neoadjuvant chemotherapy in stage II/III rectal cancer.

EXPERT-C(24)	High-Risk	CAPOX x 4 \rightarrow CRT	44	9%
		CAPOX Cetux x 4 \rightarrow CRT	46	11%
AVACROSS(25)	High-Risk	$CAPOX + Bev x 4 \rightarrow CRT$	45	36% (22-51%)
		+Bev		
GCR-3(1)	High Risk	CAPOX x 4 \rightarrow CRT	59	14.3% (6.4-26%)
FOWARC(26)	Stage II/III	Inf5FU→CRT→Inf5FU	130	13.1%
		FOLFOX6→CRT-	141	29.1%
		Ox→FOLFOX6		

High Risk: stage II/III rectal cancer with radiographic high-risk features; 5x5 RT: 25 Gy in five fractions of 5 Gy; CRT: chemoradiation (50.4 Gy in 28 fractions of 1.8 Gy plus fluorouracil based chemotherapy); Cetux: Cetuximab; Bev: Bevacizumab;

14.2 Sample Size

In table 2, the NAR scores of comparable patients enrolled in the phase III R04 study (27) and treated with long-course chemoradiation are presented (personal communications [name]). Patients with cT3N0 tumors and similar in stage to those to be enrolled in the proposed concept achieved a NAR score of 14.59 (SD 13.41). Prospective data suggests a 5.8 reduction in NAR score would be a clinically significant improvement in long terms outcomes. (15) For declared target 5.8 NAR reduction from 14.59 to 8.79 a sample size of 24 patients would be required, one-sided alpha=0.1 and beta=0.2 (Power 80.2%). Assuming an ineligibility rate of 10%, the final sample size is **27**.

Patients who pursue a course of watch and wait remain evaluable on study and will be classified as having a ypT0N0 response for the purposes of the NAR score if they do not proceed to TME surgery within 24 months of cycle 6 day 14.

R04 similar subgroup	Inclusion	Preoperative Therapy	Ν	ypT0N0 Rate	NAR Score
	cT1-3 cN any	LRT 50.4/25 plus Fluorouracil	631	18.4%	15.77 SD 14.17
	cT3 Non-Low	"	402	18.4%	16.05 SD 14.32
	cT3 cN0 Non-Low	"	293	20.2%	14.59 SD 13.41

Table 12. pCR and NAR scores in R04 patients.

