1.3 Study Overview

The study investigators hypothesize that TASOX can be safely and efficaciously delivered after short course radiation, resulting in significant pathologic downstaging, allowing for an R0 pelvic resection, and providing local control in appropriately selected stage II/III rectal cancer patients treated with contemporary TME-based surgery. It is expected that 3 months (6 cycles) of TASOX at standard doses will allow total neoadjuvant therapy introducing a new systemic agent, a shorter duration of pre-operative radiation and timely delivery of pre-operative systemic therapy. It is anticipated that if this study meets its primary endpoint, the strategy will be prospectively compared to long-course chemoradiation with capecitabine and that the reduced duration of radiation and the introduction of a new systemic agent will improve outcomes for appropriately selected patients with stage II/III rectal cancer.

In this phase II study patients will be treated with short-course preoperative irradiation (25 Gy in five fractions of 5 Gy) followed by 6 (six) 2-week cycles of TASOX followed by total mesorectal excision (TME) for patients with resectable rectal cancer (clinical T3c/dN0, T3c/dN1, T2N1). Eligible study subjects include adults who are candidates for curative intent sphincter-sparing surgery and lack high risk features such as tumor encroaching upon the mesorectal-fascia or low tumors who need an Abdominal-Perineal Resection (APR). The primary measurement of efficacy will be the Neoadjuvant Rectal (NAR) score, a validated surrogate of local and systemic disease control in stage II/III rectal cancer (17).

Figure 1. NAR Score derivation.

$NAR = \frac{[5 \ pN - 3(cT - pT) + 12]^2}{9.61}$

Fig. 1

Calculation of the neoadjuvant rectal (NAR) score. cT is an element of the set {1, 2, 3, 4}, pT is in {0, 1, 2, 3, 4}, and pN is in {0, 1, 2}. cT clinical tumor stage, pT pathologic tumor stage, pN pathologic nodal stage

The required elements of the NAR score will be prospectively collected as defined in the protocol.

[figure not shown]

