2.3 Study Schema

3.0 REGISTRATION

3.1 Inclusion Criteria

- 3.1.1 Age of at least 18 years.
- **3.1.2** Newly diagnosis of rectal adenocarcinoma.
- **3.1.3** ECOG Performance Status (PS): 0, 1 or 2.

3.1.4 Candidate for sphincter-sparing surgical resection prior to initiation of neoadjuvant therapy according to the primary surgeon.

- **3.1.5** Clinical Stage: T1/N1, T2/N1, T3/N1, T3 a/b/c/dN0.
- 3.1.6 Absence of metastatic disease.
 - Clinical staging is based on physical exam by the primary surgeon, CT scan of the chest/abdomen, and pelvic MRI.
 - Node positivity determination: Entry criteria nodes will be measured in short-axis diameter and for the purposes of study entry will be considered positive if 8 mm or greater in short axis.
 - Radiographic N2 status is estimated as: 4 or more nodes that measure 8mm or more in short-axis.
 - **Radiographic N1** status is estimated as: fewer than 4 lymph nodes that measure 8 mm or greater in short axis but 1 or more lymph nodes that measure 8 mm or greater.
 - Nodal Metastatic Disease: nodal stations considered suspicious for metastatic disease (M1) for rectal cancer are common iliac, external iliac and inguinal nodes.

3.1.7 Ability to perform a curative intent sphincter-sparing TME resection at diagnosis.

3.1.8 The following laboratory values obtained ≤ 28 days prior to registration.

- Platelet count \geq 100,000/mm3
- Hemoglobin > 8.0 g/dL
- Total bilirubin ≤ 1.5 x upper limit of normal (ULN)
- SGOT (AST) < 3 x ULN
- SGPT (ALT) \leq 3 x ULN
- Creatinine <1.5 x ULN

3.1.9 Negative pregnancy test done \leq 7 days prior to registration, for women of childbearing potential only.

3.1.10 A patient of child-bearing potential is willing to employ adequate contraception. It includes any of the followings: abstinence, oral contraceptives, implantable hormonal contraceptives, or double barrier method (diaphragm plus condom). See exclusion criterion 3.2.8 3.1.11 Provide informed written consent.

3.1.12 Willing to return to enrolling medical site for all study assessments.

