3.2 Exclusion Criteria

- **3.2.1** Clinical T4 tumors.
- **3.2.2** Clinical N2 disease estimated as four or more lymph nodes that are ≥ 8 mm.
- **3.2.3** Primary surgeon indicates need for abdominoperineal (APR) at baseline.

3.2.4 Tumor is causing symptomatic bowel obstruction or patients who have had a temporary diverting ostomy are ineligible.

3.2.5 Chemotherapy within 5 years prior to registration. (Hormonal therapy is allowable if the disease free interval is \geq 5 years.)

3.2.6 Any prior pelvic radiation.

3.2.7 Any of the following because this study involves an agent that has known genotoxic, mutagenic and teratogenic effects:

- Pregnant women
- Nursing women
- Men or women of childbearing potential who are unwilling to employ adequate
- contraception

3.2.8 Co-morbid illnesses or other concurrent disease which, in the judgment of the treating investigator obtaining informed consent, would make the patient inappropriate for entry into this study or interfere significantly with the proper assessment of safety and toxicity of the prescribed regimens.

3.2.9 Patients with threatened radial margins, defined as tumors with distance of 1mm or less, or adherent to the mesorectal fascia.

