7.0 RADIOLOGIC IMAGING

The primary interpretation of all imaging studies will occur at each site, and each site will make the initial determination for each patient as to:

- 1. Study eligibility
- 2. Initial MRI study adequacy
- 3. Baseline TNM status
- 4. Post-treatment T and N status

Estimated Radiographic T Stage (Using AJCC 8th Edition Definitions):

This should be estimated as T1, T2, or T3c/d (ie. T3c, >5 to 15 mm; T3d, >15 mm beyond muscularis propria). T4 tumors are ineligible. See APPENDIX I.

Estimated Radiographic N Stage:

For purposes of achieving consistent interpretation in this protocol:

Node positivity determination: Entry criteria nodes will be measured in short-axis diameter and for the purposes of study entry will be considered positive if 8mm in short axis.

Radiographic N2 status is estimated as: 4 or more nodes that measure 8mm or more in short-axis. Radiographic N1 status is estimated as: fewer than 4 lymph nodes that measure 8 mm or greater in short axis but 1 or more lymph nodes that measure 10 mm or greater.

Distance of the Tumor from the Mesorectal Fascia Reflection: patients with tumors with a distance of 1mm or less, or adherent to the mesorectal fascia reflection have threatened radial margins and are ineligible.

Presence of Distant Disease:

Nodal stations considered suspicious for metastatic disease (M1) for rectal cancer are: common iliac, external iliac and inguinal nodes.

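### The null NAR of 14.59 is a cT3 cN0 benchmark, but cN1 patients are eligible, so the stated 80.2% power describes only an all-cT3N0 cohort

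*Combined protocol and SAP*

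**What the plan says.** Section 14.2 takes its only benchmark from the third row of Table 12, R04 cT3 cN0 Non-Low (N=293, mean 14.59, SD 13.41): "Patients with cT3N0 tumors and similar in stage to those to be enrolled in the proposed concept achieved a NAR score of 14.59". It continues: "For declared target 5.8 NAR reduction from 14.59 to 8.79 a sample size of 24 patients would be required", at one-sided alpha 0.1 with stated power 80.2%. Allowing 10% ineligibility gives 27.

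Eligibility is wider than that row. Criterion 3.1.5 reads "Clinical Stage: T1/N1, T2/N1, T3/N1, T3 a/b/c/dN0", so three of its four stage groups are node-positive. Section 1.3 gives a different list, "clinical T3c/dN0, T3c/dN1, T2N1", which also includes cN1. Section 7.0 says of radiographic T stage: "This should be estimated as T1, T2, or T3c/d". Criterion 3.2.2 excludes "Clinical N2 disease estimated as four or more lymph nodes".

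The other two rows of Table 12 are cT3 Non-Low of any cN (N=402, mean 16.05, SD 14.32) and cT1-3 of any cN (N=631, mean 15.77, SD 14.17). The plan sets no limit on the cN1 share, does not adjust the null for stage, and gives no power for any other mix.

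**The concern.** In a single-arm trial against historical controls, the benchmark is the whole comparison. If node-positive patients have higher NAR scores on standard treatment, a cohort that includes them starts above 14.59. Part of the treatment effect is then spent on reaching the null.

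The cT coding adds a second mismatch. The NAR formula in section 1.3 depends on cT, so a mean from cT3 patients does not carry over directly to T1N1 or T2N1.

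Two things are at stake. An active regimen could be missed, although section 1.3 makes a later comparative trial depend on this endpoint. And the result would reflect the stage mix that happens to enrol as well as the treatment.

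**Working it through.** **Plan's own figure.** Section 14.2 does not name the test. A one-sample z-test gives power = Φ((14.59 − T)·√24/SD − 1.2816), where T is the treated mean. With T=8.79 and SD 13.41 this is 79.9%, and the required n is 24.1. A one-sample t-test gives 78.8% at n=24. Then 24/0.9 = 26.7, rounded up to 27. The stated 80.2% is sound for these inputs.

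**Group left over in Table 12.** Treating the cT3 cN0 row as nested in the cT3 Non-Low row:
- Size: 402 − 293 = 109, or 27% of 402.
- Mean: (402×16.05 − 293×14.59)/109 = 19.97. Subtracting sums of squares in the same way gives SD 15.93.
- Excess over cN0: 5.38, SE √(15.93²/109 + 13.41²/293) = 1.72, 95% CI 2.0 to 8.7.

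These 109 patients are assumed node-positive and may include cN2.

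**Power against 14.59 at n=24.** The documents do not give the cN1 share, the cN1 mean, or how the target applies to a mixed cohort, so three alternatives are shown:
- treated mean 8.79 whatever the mix;
- the same proportional reduction (8.79/14.59);
- a 5.8-point drop from the mix's own mean.

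For the R04 row, SD is 14.32 and T is 8.79, 9.67 or 10.25. For the other rows the mean is 14.59 + excess × cN1 share, with the mixture SD from 13.41 and 15.93. Excesses of 5.38, half of that (2.69), and the lower confidence limit (2.0) are used.

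| Cohort | Mean 8.79 | Proportional | 5.8 below own mean |
|---|---|---|---|
| R04 cT3 Non-Low (27% not cN0) | 75.9% | 65.6% | 58.1% |
| 4 of 24 cN1, excess 5.38 | 77.2% | 71.2% | 66.8% |
| 4 of 24 cN1, excess 2.69 | 77.7% | 74.8% | 72.7% |
| 4 of 24 cN1, excess 2.0 | 77.8% | 75.6% | 74.1% |
| 1 of 24 cN1, excess 5.38 | 79.2% | 77.8% | 76.8% |
| 1 of 24 cN1, excess 2.69 | 79.3% | 78.6% | 78.1% |
| 1 of 24 cN1, excess 2.0 | 79.3% | 78.8% | 78.5% |

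**False positives if the regimen only matches R04.** With T=16.05 and SD 14.32 the rate is 3.7%. With T=15.77 and SD 14.17 it is 4.6%. With 4 of 24 cN1 it is 5.5%, 7.5% or 8.1% for the three excesses. All are below the nominal 10%.

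**cT coding.** At ypT0N0, NAR is (12 − 3cT)²/9.61: 0.94 for cT3, 3.75 for cT2, 8.43 for cT1. These are minimum scores, not expected means. They show that cT matters, not which way the mean of T1N1 or T2N1 patients would shift.

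**Two tempting replacement nulls.**
- Fixed 16.05 with an all-cN0 cohort: Φ(1.46·√24/13.41 − 1.2816) = 22.7% false positives.
- 14.59 and 19.97 weighted by enrolled shares, when the true excess is 2.0. With 4 of 24 cN1 the null is 15.49 against a true mean of 14.92 (SD 13.88), giving about 14%. At 27% cN1 it is 16.05 against 15.13 (SD 14.17), giving about 17%.

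**The case against.** The strongest reply is that the direction is not proven. Table 12 has no cN1-only row, and its higher rows may include cN2, which the trial excludes. The trial also excludes threatened radial margins (3.2.9) and symptomatic obstruction (3.2.4), and requires sphincter-sparing candidacy (3.1.4, 3.1.7). Table 12 shows only the Non-Low restriction on the two cT3 rows. Such selection could lower expected NAR and offset a cN1 excess. This stands, and it is why the claim is probable rather than certain.

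A second reply is that the plan's alternative is a mean of 8.79. On that reading the R04 mix costs about 4 points of power, all from the larger SD. This also stands. A reader might infer that true power is 58%, but that needs a treated mean of 10.25, which the plan never states, and an R04-like node-positive share, which the documents do not give.

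A third reply is that a strict benchmark is defensible in a phase II screen. That holds for a benchmark chosen deliberately. Here section 14.2 presents the cN0 row as matching the enrolled stages, and its power figure ignores the mismatch.

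The conservatism is not guaranteed either. Patients on watch and wait without TME within 24 months "remain evaluable on study and will be classified as having a ypT0N0 response for the purposes of the NAR score", which pushes NAR the other way. That is a separate point and is not quantified here.

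**Conclusion.** The concern holds in a limited form. The benchmark and the 80.2% describe cT3 cN0 patients, while the eligibility criteria define a wider cohort. On Table 12 the null is probably too low for a mix that includes cN1.

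At n=24 the loss runs from a point or so (1 of 24 cN1, treated mean 8.79) to about 22 points (R04 mix, 5.8 below 16.05). If the planned 8.79 is reached at the R04 mix, it is about 4 points.

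These figures assume that R04 SDs apply, that the 109 leftover patients stand in for cN1, and that cT3 data stand in for T1N1 and T2N1. The 15.77 row may also include low tumours.

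The documents do not support saying that the 80.2% is miscalculated, that the mismatch inflates false positives, or that the null should simply be raised to 16.05. Correction before analysis is warranted because a stage weighting chosen after the data are seen would be open to challenge.

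**What to change.** Before analysis, ask the source of Table 12 for R04 Non-Low NAR means by cN (N0, and N1 without N2), and by cT where numbers allow.

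**If supplied:** pre-specify the test as mean observed minus stage-expected NAR against 0, at one-sided 0.1, and restate power at n=24. For a 5.8-point reduction at the R04 mix, the within-stratum SD is √((293×13.41² + 109×15.93²)/402) = 14.14. Power is then about 77% by z-test or 76% by t-test. Counting reference error (SE about 0.7) lowers the z-test figure to about 75%. If cells for T1N1 or T2N1 are too sparse, use cN only.

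**If not supplied:** keep 14.59 as the primary null, labelled as a cT3 cN0 benchmark. Restate power as a range, report the enrolled cT and cN mix, and show a sensitivity analysis over a range of cN1 excess, for example 0, 2.0, 2.7 and 5.4. Do not rely on 19.97 alone or on a fixed 16.05.

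**In either case:** reconcile the stage lists in 1.3, 3.1.5 and 7.0, and the N1 node-size rules. Section 3.1.6 needs at least one node of 8 mm or more and section 7.0 at least one of 10 mm or more. Appendix I needs fewer than four nodes of 10 mm or more, with at least one of 8 mm or more. A patient with a single 9 mm node is N1 under 3.1.6 and Appendix I but not under 7.0, so the stratum is undefined until these agree.

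**Cost:** SAP wording, one data request and, under the fallback, one sensitivity analysis, with no added patients. Restoring 80% power is optional. It needs 27 evaluable by z-test (27/0.9 = 30 enrolled) or 28 by t-test (28/0.9 = 31.1, so 32 enrolled).

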9. Recommendation: Surgery should be performed within 10 weeks AFTER the 6th cycle of neoadjuvant TASOX, and restaging investigations should be obtained within 8 weeks (56 days) AFTER day #14, cycle 6.

10. Adverse Events form to be completed at the start of radiation therapy.

11. Pelvic MRI should be booked within 56 days of completion of cycle #6 of TASOX, i.e. within 1-56 days AFTER day #14, cycle 6.

12. Patients that achieve a complete or near complete Clinical Response (cCR or ncCR) may choose to pursue a course of watch and wait with agreement of their treating surgeon. A thorough discussion is recommended with their surgeon concerning the risks and benefits of watch and wait and both they and their physician agree with the intended approach. Patients that pursue a course of watch and wait remain evaluable on study and will be classified as having a ypT0N0 response for the purposes of the NAR score if they do not proceed to TME surgery within 24 months of completing cycle 6, day 14.

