6.4 Surgical Therapy

Standard surgical therapy with a total mesorectal excision (TME) is to be done within 10 weeks of completion of cycle #6 of chemotherapy with TASOX with staging to be done within 8 weeks after day 14 of cycle 6.

Operative approach will be at the discretion of surgeon, and can include either laparoscopic (or robotic-assisted laparoscopic) or open anterior or low anterior resection with or without temporary fecal diversion. Preoperative antibiotics and bowel preparation are institution specific will be at the discretion of the operating surgeon. The mobilization of the proximal colon and splenic flexure may be performed by laparoscopic, laparoscopic-assisted, robotic-assisted or hand-assisted at the discretion of the surgeon to limit the incision to the lower abdomen. The pelvic dissection should include TME, division of inferior mesenteric vascular pedicle, transection of the specimen, and anastomosis. Anastomosis may be stapled or hand-sewn. Variation in technical approaches will be at the surgeon's discretion as they are impacted by the patient's body habitus, incisions, and tumor location.

Patients that achieve a complete or near complete Clinical Response (cCR or cCR), may choose to pursue a course of watch and wait with agreement of their treating surgeon. A thorough discussion is recommended with their surgeon concerning the risks and benefits of watch and wait and both they and their physician agree with the intended approach. Patients that pursue a course of watch and wait remain evaluable on study and will be classified as having a ypT0N0 response for the purposes of the NAR score if they do not proceed to TME surgery within 24 months of completing cycle 6, day 14.

Surgical Complications

Perioperative and postoperative complications will be collected and submitted; see Section 10.0.

Early complications (within 30 days)

Morbidity and mortality will be closely monitored and recorded using the study data forms with the following definitions:

- 1. Pulmonary, urinary tract, and intraabdominal infections will be defined by the need for antibiotic treatment and/or interventional radiology drainage.

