10.0 ADVERSE EVENT (AE) REPORTING AND MONITORING

10.1 Adverse Event Characteristics

CTCAE term (AE description) and grade: The descriptions and grading scales found in the revised NCI Common Terminology Criteria for Adverse Events (CTCAE) version 5.0 will be utilized for AE reporting. All appropriate treatment areas should have access to a copy of the CTCAE version 5.0.

Adverse event monitoring and reporting is a routine part of every clinical trial. First, identify and grade the severity of the event using the CTCAE v5.0. Next, determine whether the event is expected or unexpected and if the adverse event is related to the medical treatment or procedure. With this information, determine whether the adverse event must be reported as an expedited report.

The safety reporting period begins after the subject has signed the informed consent and ends 28 days after the last dose of study drug. It is only required that SAEs be reported following consent and prior to radiation therapy initiation, while all AEs (serious and non-serious) be reported thereafter.

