11.0 TREATMENT EVALUATION

11.1 Guidance for radiological tumor evaluation

Repeat non-contrast pelvic MRI to rule out progressive disease and ensure surgical resectability is required as per standard of care recommendations (22). Pelvic MRI should be booked within 56 days of completion of cycle #6 of TASOX, ie within 1-56 days AFTER day #14, cycle 6. Radiographic tumor staging should be performed and reported per the initial, staging MRI. See APPENDIX I for guidance.

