11.4 Definition of pathologic stage

Derivation of the Neoadjuvant response (NAR) score requires pathologic staging information from the TME resection specimen staged according to the AJCC8th edition schema:

T describes how far the main (primary) tumor has grown into the wall of the intestine and whether it has grown into nearby areas. Because this information will be ascertained from the surgical pathology report it is denoted with a prefix "p". Because it is ascertained after neoadjuvant treatment, the prefix "y" is also added (e.g., ypT3).

Tx Primary tumor cannot be assessed

- T0 No evidence of primary tumor
- Tis Carcinoma in situ: intraepithelial or invasion of lamina propria
- T1 Tumor invades submucosa
- T2 Tumor invades muscularis propria
- T3 Tumor invades through the muscularis propria into pericolorectal tissues
- T4a Tumor penetrates to the surface of the visceral peritoneum

T4b Tumor directly invades or is adherent to other organs or structures

N describes the extent of spread to nearby (regional) lymph nodes based on the

rectal resection specimen. The prefix "yp" is added as described for T status.

- Nx Regional lymph nodes cannot be assessed
- N0 No regional lymph node metastasis
- N1 Metastasis in 1-3 regional lymph nodes
- N2 Metastasis in 4 or more regional lymph nodes

11.5 Definition of Pathological Complete Response (pCR):

A pCR must include no gross or microscopic tumor identified anywhere within the surgical specimen. This must include no evidence of malignant cells in the primary tumor specimen **and** no lymph nodes that contain tumor.

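### The watch-and-wait scoring rule gives a patient with documented but unresected local or nodal regrowth the best possible NAR score, an error that can only favour success

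*Combined protocol and SAP*

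**What the plan says.** Section 4.0 (note 12) opens watch and wait to incomplete as well as complete responders: "Patients that achieve a complete or near complete Clinical Response (cCR or ncCR) may choose to pursue a course of watch and wait", with the treating surgeon's agreement. Section 6.4 then gives the scoring consequence: "Patients that pursue a course of watch and wait remain evaluable on study and will be classified as having a ypT0N0 response", on condition that TME does not take place within 24 months of cycle 6 day 14. Section 14.2 repeats the rule beside the sample size: such a patient is "classified as having a ypT0N0 response for the purposes of the NAR score if they do not proceed to TME surgery within 24 months" of that date. None of the three places adds a condition on pelvic status.

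Elsewhere the score rests on a specimen. Section 11.4 states: "Derivation of the Neoadjuvant response (NAR) score requires pathologic staging information from the TME resection specimen". A watch-and-wait patient who never has TME has no specimen, so the rule supplies the pathologic stage.

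Two other places bear on what would be known about such a patient. Note 1 to the schedule in Section 4.0 calls for an assessment when disease progresses and when a patient withdraws or is taken off study. The schedule table itself has no watch-and-wait visit. Its only post-treatment pelvic MRI falls within 56 days of the end of cycle 6, and its last column is the post-surgery visit.

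**The concern.** The ypT0N0 score is a reasonable convention for a sustained clinical complete response. As written, however, it depends on whether TME took place and not on whether tumour is present. A patient whose tumour regrows locally or in the nodes, and who declines or cannot have TME, would be scored as having no tumour in bowel wall or nodes, even with the regrowth in the record.

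NAR is the only primary endpoint. Its mean in about 24 patients is compared with a fixed historical value, so there is no concurrent arm in which the same convention could cancel. An error that always moves the mean downward moves it towards a declared success.

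**Working it through.** **Inputs.** The NAR formula is in Section 1.3, Figure 1. Eligible stages are cT1 to cT3 (3.1.5; T4 is excluded by 3.2.1). Section 14.2 gives the benchmark 14.59, SD 13.41, target reduction 5.8, one-sided alpha 0.10, n=24 and stated power 80.2%. The documents do not name the primary test. A one-sample z test is assumed, with a one-sample t test as a check.

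**The plan's own figure.** n = (13.41 × (1.2816 + 0.8416) / 5.8)² = 24.10. At n=24 the standard error is 13.41/√24 = 2.737, and power is Φ(5.8/2.737 − 1.2816) = 79.9% (78.8% by t test), close to the stated 80.2%. Inflating for 10% ineligibility, 24/0.9 = 26.7, which rounds up to 27. The sample size is not in question.

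**Direction.** NAR = [5pN − 3(cT − pT) + 12]²/9.61. At pT0 pN0 the bracket is 12 − 3cT, that is 3, 6 and 9 for cT3, cT2 and cT1. It is positive and rises with both pT and pN, so ypT0N0 is the unique minimum for each cT:

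- cT3: 9/9.61 = 0.94
- cT2: 36/9.61 = 3.75
- cT1: 81/9.61 = 8.43

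Any other true stage scores higher, so wrongly assigning ypT0N0 can only lower the mean.

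**Size, illustrative.** Suppose k of 24 patients, all cT3, are wrongly scored 0.94, the correctly scored mean is 14.59 (no benefit), and the SD stays at 13.41. Success is declared when the mean falls by 1.2816 × 2.737 = 3.51, to about 11.08. The downward shift per patient is (true NAR − 0.94)/24, and the false-success rate is Φ(k × shift/2.737 − 1.2816).

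| True stage (cT3) | NAR | Shift per patient | k=1 | k=3 | k=3, t test |
|---|---|---|---|---|---|
| ypT1N0 | 3.75 | 0.117 | 10.8% | 12.4% | 12.4% |
| ypT0N1 | 6.66 | 0.238 | 11.6% | 15.4% | 15.3% |
| ypT2N0 | 8.43 | 0.312 | 12.2% | 17.4% | 17.2% |
| ypT3N0 | 14.98 | 0.585 | 14.3% | 26.1% | 25.7% |

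ypT3N0 is the largest case tabulated, not an upper bound: ypT3N1 would score 289/9.61 = 30.07.

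**What is not misclassification.** The score uses only "cT clinical tumor stage, pT pathologic tumor stage, pN pathologic nodal stage". Later metastasis or death without pelvic tumour is therefore not an error in the score.

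**The case against.** The rule is narrower than it first looks. It covers only patients with a complete or near-complete clinical response whose surgeon agreed, and two years without TME is some evidence of a sustained response. For the rule to fail, regrowth must occur and TME must also not be done in the window. Regrowth resected by TME within 24 months is outside the rule. No document gives a watch-and-wait or regrowth rate, so even one affected patient is an assumption, and three is a stronger one. All of this stands and limits the size of the point. It does not remove the case in which recorded regrowth is scored as no tumour.

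Three stronger readings are tempting, and the documents do not support them.

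- A reader might infer that regrowth would go unseen because no watch-and-wait visit is scheduled. Note 1 to the schedule requires assessment at progression, withdrawal or removal, so some regrowth would be documented. What is missing is any link from that assessment to the score.
- A reader might infer that the watch-and-wait policy as a whole biases the trial towards success. Patients who have TME before 24 months are scored from a specimen that may be late and may raise NAR, so the net effect is not known.
- A reader might infer that every near-complete responder, or every patient with undocumented status, is wrongly scored. The documents do not show their true stage. Imaging stage, which Appendix I itself describes as inexact, would exchange one possible misclassification for another.

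**Conclusion.** The point holds for documented, unresected local or nodal regrowth. The stated rule gives such a patient the best score available for that cT, and the error runs in one direction, towards success against 14.59. This should be corrected before the primary analysis.

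The size cannot be fixed from the documents. With one affected cT3 patient the false-success rate would be 10.8% to 14.3% instead of 10%. With three it would be 12.4% to 26.1%. The higher figures in each range need residual disease of ypT3N0, the least likely of the tabulated cases among selected good responders. These figures assume n=24, an SD held at 13.41, a one-sample z test and the stated numbers of misclassified patients. A small to moderate effect is a fair reading of the more plausible cases. The direction rests on the formula alone and needs none of these assumptions.

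**What to change.** Change scoring and analysis only, with no change to patient management.

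1. In Sections 4.0 (note 12), 6.4 and 14.2, add to the ypT0N0 rule the condition that no local or nodal regrowth is documented within the 24-month window. Record the date of the last pelvic assessment.
2. Score documented unresected regrowth by its documented clinical T and N stage, labelled as clinical. Section 7.0 already has sites determine "Post-treatment T and N status". Node-only regrowth needs a T0 code, because the T lists in Section 7.0 and Appendix I start at T1.
3. For persistent near-complete response, or pelvic status not documented to 24 months (including patients assessed early and then lost), keep ypT0N0 in the primary analysis so that it stays defined. Report how many there are. Repeat the primary test with them scored pT=cT, pN0 (144/9.61 = 14.98 for every cT), and state whether the conclusion holds.
4. Report a resected-only analysis as descriptive, noting that it omits the best responders.

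**Cost.** Three wording changes, one stage code, abstraction of pelvic status and dates from existing records, and two short analyses. No further patients are needed. Mean NAR becomes less favourable by 0.12 (ypT1N0) to 0.59 (ypT3N0) per reclassified cT3 patient, and clinical stage is less exact than specimen stage. The analysis at 14.98 is deliberately harsh. If the rescored cT3 patients were truly ypT0N0, power would fall from 79.9% to Φ((5.8 − 0.585)/2.737 − 1.2816) = 73.4% with one patient and 57.8% with three. It therefore belongs in a sensitivity analysis and not in the primary rule.
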